- NB – in the event of an exclusion to carrying out bronchial aspirate, (i.e: Significant hypoxia or instability precluding ventilator disconnection
- Transcutaneous oxygen saturation of <95% on 60% oxygen
- Risk of bleeding
- Pneumothorax);

As long as there is no contra-indication to carrying out NPA or nasal SAM sampling, then these children can still be included in the study, but will not require bronchial sampling.

Control Group 1

Inclusion criteria

- Babies, aged 2 weeks-24 months, attending routine outpatient appointments or undergoing elective surgical procedures.

Exclusion criteria

- Any respiratory symptoms
- All other exclusion are the same as Groups 1 and 2

Control Group 2

Inclusion criteria

- Infants aged 2 weeks-24 months.
- Infants ventilated on the PICU for any condition
- Confirmed RSV negative by PCR of respiratory tract samples

Exclusion Criteria

- All exclusions are the same as Group 3
- In addition – any concern about raised intracranial pressure

DATA STORAGE

Anonymised data will be stored in Redcap in the Department of Paediatrics at Imperial College London. The database will be password protected and will be web-based. Only those directly involved in the study will be able to access the data. Individuals will only be identified on the database by their unique alphanumeric identifier; data relating to the subjects' names to this identifier will be stored separately. Any data generated may be stored indefinitely and shared with other researchers outside of the participating sites. This will be done through databases such as ENA and EGA. Any data made available on these databases will be strictly confidential.

DATA ANALYSIS

Levels of inflammatory mediators (e.g. cytokines as pg/ml) across the patient groups will be presented as:

- Raw data: linear and log plots as appropriate
- Box-whisker plots: median/quartile/range
- Heat maps to show correlation between levels of mediators

Statistical analysis will be performed to demonstrate significance of levels of individual biomarkers and molecular signatures.

Data and all appropriate documentation will be stored for a minimum of 10 years after the completion of the study, including the follow-up period.

WITHDRAWAL CRITERIA

Any clinically significant side effects during procedures or withdrawal of consent by the parents or guardians of participants.

ADVERSE EVENTS

DEFINITIONS

Adverse Event (AE): any untoward medical occurrence in a patient or clinical study subject.

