Serious Adverse Event (SAE): any untoward and unexpected medical occurrence or effect that:

- **Results in death**
- **Is life-threatening** – refers to an event in which the subject was at risk of death at the time of the event; it does not refer to an event which hypothetically might have caused death if it were more severe
- **Requires hospitalisation, or prolongation of existing inpatients' hospitalisation**
- **Results in persistent or significant disability or incapacity**
- **Is a congenital anomaly or birth defect**

Medical judgement should be exercised in deciding whether an AE is serious in other situations. Important AEs that are not immediately life-threatening or do not result in death or hospitalisation but may jeopardise the subject or may require intervention to prevent one of the other outcomes listed in the definition above, should also be considered serious.

REPORTING PROCEDURES

All adverse events should be reported. Depending on the nature of the event the reporting procedures below should be followed. Any questions concerning adverse event reporting should be directed to the Chief Investigator in the first instance.

Non serious AEs

All such events, whether expected or not, should be recorded.

Serious AEs

An SAE form should be completed and faxed to the Chief Investigator within 24 hours. However, relapse and death due to hospitalisations for elective treatment of a pre-existing condition do not need reporting as SAEs.

All SAEs should be reported to the REC where in the opinion of the Chief Investigator, the event was:

- 'related', ie resulted from the administration of any of the research procedures; and
- 'unexpected', ie an event that is not listed in the protocol as an expected occurrence

Reports of related and unexpected SAEs should be submitted within 15 days of the Chief Investigator becoming aware of the event, using the NRES SAE form for non-IMP studies. The Chief Investigator must also notify the Sponsor of all SAEs.

Local investigators should report any SAEs as required by their Local Research Ethics Committee, Sponsor and/or Research & Development Office.

Contact details for reporting SAEs

[contact], attention [name]

Please send SAE forms to:

St, Mary's Hospital,

[name],

[name]

London

[name]

[contact] (Mon to Fri 09.00 - 17.00)

ASSESSMENT AND FOLLOW-UP

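### The SAE definition includes 'unexpected', which contradicts the REC reporting step and, on its ordinary meaning, takes serious but foreseeable events off the 24-hour and Sponsor reporting routes

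*Combined protocol and SAP*

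**What the plan says.** All the relevant text is in the Adverse Events section of the combined protocol and SAP.

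- **Definitions, AE:** "any untoward medical occurrence in a patient or clinical study subject". There is no condition on expectedness.
- **Definitions, SAE:** "any untoward and unexpected medical occurrence or effect that" meets one of five outcomes (death, threat to life, admission or longer stay, lasting disability, congenital anomaly). A medical-judgement clause adds other important events that fall short of death, immediate threat to life or admission. That clause has no expectedness condition.
- **Reporting Procedures, opening:** "All adverse events should be reported".
- **Non serious AEs:** "All such events, whether expected or not, should be recorded".
- **Serious AEs, first step:** "An SAE form should be completed and faxed to the Chief Investigator within 24 hours".
- **Serious AEs, REC step:** SAEs go to the REC, within 15 days, if the Chief Investigator judges them related to a research procedure and unexpected. Unexpected is explained here, and only here, as "an event that is not listed in the protocol as an expected occurrence".
- **Serious AEs, Sponsor step:** "The Chief Investigator must also notify the Sponsor of all SAEs".

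**The concern.** Seriousness and expectedness are separate properties of an event. Seriousness normally decides whether the event is escalated at all, and expectedness decides how far it goes. Here expectedness is used at both stages. Taken at its word, the definition gives a mild expected event an explicit recording rule, while a life-threatening expected event has no matching rule. It is not an SAE, and it does not belong under the non-serious heading.

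What is at stake is prompt central sight of serious events that staff might regard as part of the illness or as a known effect of sampling. Clinical tolerability of the sampling methods is part of aim 1. The Assessment and Follow-up section plans no follow-up when sampling is well tolerated, so reporting at the time of the event carries much of the safety information. A serious event that recurs because it is foreseeable is one the Chief Investigator and Sponsor would want to see early.

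**Working it through.** The plan gives no event rate or count on this point, so the check is one of logic, with one piece of arithmetic for context.

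**1. The two rules side by side.** Let S be events with a serious outcome, U unexpected events and R events related to a research procedure.

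- As written: SAE = S and U. REC report = SAE and R and U = S and U and R, which is the same as SAE and R. If U means the same in both places, the REC filter on expectedness removes nothing.
- If 'unexpected' is dropped from the definition: SAE = S. REC report = S and R and U. The filter now does some work.
- The difference between the two is the set of events that are serious and expected.

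**2. What happens to a serious, expected event.** This depends on what 'unexpected' means in the definition, which does not explain it.

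- *Ordinary meaning (clinically foreseeable).* The event is not an SAE. The 24-hour form, the Sponsor notice and the REC step all depend on SAE status, so none applies. The general instruction to report all adverse events still covers it, because the AE definition has no expectedness condition. That instruction names no recipient, form or time limit.
- *The REC-step meaning (not on the protocol's list).* No list of expected occurrences appears in the text from the background section through the reference list. With an empty list every event is unexpected, every serious event is an SAE and none is lost. The word then has no effect in either place.

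The protocol does not say which meaning applies to the definition.

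**3. Whether another clause closes the gap.** The medical-judgement clause brings in important events whether or not they are expected, but it is worded for events short of death, immediate threat to life or admission. On the ordinary meaning, the gravest outcomes are therefore subject to an expectedness condition and the less grave ones are not. The separate exemption concerning elective treatment of a pre-existing condition does not turn on expectedness and does not help.

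**4. Who is exposed.** From Number and types of Subjects in the Study Design section:

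- planned total: 5 groups × 30 = 150;
- ventilated in PICU (Group 3 and Control Group 2): 2 × 30 = 60, or 60/150 = 40%;
- with the ward patients of Group 2 added: 3 × 30 = 90 inpatients by group definition, or 90/150 = 60%.

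These are headcounts of infants in whom serious events of the underlying illness are foreseeable. They are not estimates of how many events would go unreported.

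**The case against.** The strongest reply is that nothing is really lost. The Reporting Procedures open by requiring every adverse event to be reported, reporting questions go to the Chief Investigator, and recruitment is from one hospital, so divergent practice can be corrected locally. This stands in part: such events remain reportable AEs. It does not restore the 24-hour form or the Sponsor notice, which are tied to SAE status.

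A second reply is that the missing list cannot cause loss, because an empty list makes every event unexpected. That is correct. The list test also sits in the REC step, and the definition does not refer to it. The possible loss comes from the undefined word in the definition. The absent list matters because it leaves staff nothing against which to settle the meaning.

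A third reply is that the safety stakes are modest. Aim 2 concerns bronchosorption, which the Procedures section suspends for the 2016-2017 season. Bronchial aspirate is material from routine suction, and tolerability is not a listed endpoint. This is fair and limits how much weight the point should carry. Tolerability under aim 1 remains, as does nasal sampling of ventilated infants.

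A reader might infer more than the text supports. One inference is that serious expected events disappear from all reporting, so that the Chief Investigator and Sponsor would receive none; the general reporting rule contradicts that. Another is that SAE counts could not be compared between ED, ward and PICU; the plan proposes no such comparison.

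**Conclusion.** The point holds as an internal contradiction with a limited consequence. The SAE definition excludes expected events, while the REC step presupposes that they exist. On the ordinary meaning of 'unexpected', serious but foreseeable events fall outside the 24-hour, Sponsor and REC routes and are covered only by a general instruction without recipient, form or deadline. On the list-based meaning nothing is lost. The protocol does not choose between the two.

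The number of affected events cannot be estimated, because the documents give no rates for serious events or admissions. The context is 60 ventilated infants among 150 planned. The contradiction rests on the wording alone. The absence of a list is confirmed only for the protocol text from the background section onward, because earlier material was not available for review; the contradiction does not depend on it. The change is worth making because the defect is in a stated safety rule and costs little to repair.

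**What to change.** Three wording changes in the Adverse Events section:

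1. Delete 'and unexpected' from the SAE definition, so that seriousness rests on the five outcomes and the medical-judgement clause.
2. Apply relatedness and expectedness only as the filter for REC reporting.
3. Either list the expected occurrences that the REC step refers to, or state that there are none.

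The cost is a short protocol amendment and, compared with the ordinary-meaning reading, more 24-hour forms and Sponsor notices. These would include foreseeable events of the presenting illness, such as admission from the ED or a longer stay. The list in step 3 does not reduce that load, because it affects only what goes to the REC. Compared with the empty-list reading, the change adds no SAE forms.

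### The SAE exemption for elective treatment, read literally, releases some deaths from the 24-hour form although death is a listed seriousness criterion

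*Combined protocol and SAP*

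**What the plan says.** Under Adverse Events, Definitions, an SAE is an occurrence that is both untoward and unexpected and meets at least one listed criterion. The first criterion is "Results in death", with no qualification by cause. A later one begins "Requires hospitalisation, or prolongation of existing" and concerns inpatient stays. A following paragraph widens seriousness by medical judgement to "Important AEs that are not immediately life-threatening or do not result in death or hospitalisation but may jeopardise the subject".

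Under Reporting Procedures, a general line asks for every adverse event to be reported by the route that suits its nature. Non-serious events are to be recorded, with no time limit. For serious events the rule is "An SAE form should be completed and faxed to the Chief Investigator within 24 hours". The sentence directly after it is the exemption: "However, relapse and death due to hospitalisations for elective treatment of a pre-existing condition do not need reporting as SAEs".

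Three further duties follow, all worded in terms of SAEs:

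- **REC:** "All SAEs should be reported to the REC where in the opinion of the Chief Investigator, the event was" related to a research procedure and unexpected.
- **Sponsor:** "The Chief Investigator must also notify the Sponsor of all SAEs".
- **Sites:** "Local investigators should report any SAEs as required by their Local Research Ethics Committee, Sponsor" or the R&D office.

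**The concern.** The definition and the exemption pull in opposite directions for one class of event. A death that is untoward, unexpected and put down to an elective hospitalisation is an SAE by definition, yet the reporting section says it need not be reported as one.

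What is at stake is who decides the cause. The protocol leaves relatedness to the Chief Investigator's opinion, and the 24-hour form is the only specific route it gives for bringing a serious event to that person. The exemption turns on cause of death, so someone must attribute the cause before deciding whether a form is needed. The protocol does not say who does this, whether it is recorded, or whether the Chief Investigator hears of it. A wrong attribution could keep a death from the one person assigned to judge whether sampling contributed.

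**Working it through.** No arithmetic applies, because the protocol gives no event rate and the question is whether its sentences agree. The check follows one hypothetical event through the text: an untoward, unexpected death of an enrolled infant, attributed locally to an elective admission.

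1. **Is it an SAE under Definitions?** Yes. It passes the opening condition and meets the death criterion, which has no carve-out by cause.
2. **Is the 24-hour form required?** The form rule says yes. The next sentence says such a death does not need reporting as an SAE. The exemption is the more specific statement, so a reader would follow it and send no form.
3. **Does the important-events paragraph bring it back?** No. It is written for events that do not result in death or hospitalisation.
4. **Does it reach the REC?** Only if it is handled as an SAE and the Chief Investigator judges it related and unexpected. Without a form, nothing in the text prompts that judgement.
5. **Does it reach the Sponsor?** The text does not settle this. If the death remains an SAE by definition, the Sponsor duty formally stands, but the Chief Investigator can act on it only if told. If the exemption removes the death from the SAE class, the duty lapses. The local-investigator sentence has the same ambiguity.
6. **What remains?** The general line on reporting every adverse event. It points to the procedures below it, where the only other branch is for non-serious events, and that branch has no time limit.

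**Can the sentence be read differently?** A death due to a hospitalisation is odd wording, and two exemptions may have been run together: one for relapse and death, one for elective admissions. Relapse is not explained in the text available to me. The protocol does not show what was intended, but on either reading some deaths are exempt.

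**Can it reach enrolled infants?** Yes. The inclusion criteria for Control Group 1 admit infants undergoing elective surgery. Control Group 2 takes infants ventilated for any condition, which does not rule out ventilation after elective surgery, though the protocol does not say that any such infant will be enrolled.

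**Minor wording point.** Expectedness appears twice, in the SAE definition and in the REC filter. A serious event judged expected would therefore fit neither the serious nor the non-serious branch. I found no list of expected occurrences, but the opening part of the document was not available to me, so its absence cannot be held against the plan. No affected event is shown.

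**The case against.** The best defence is that a general definition followed by a named exception is ordinary drafting. On that view the sentence waives only the SAE form and its time limit, while the general reporting duty continues. Part of this stands: exempt deaths are not released from all reporting. But the exception is attached to the most serious criterion, its wording is unclear, and it removes the timed step that prompts a relatedness judgement.

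A second defence is that the reach is narrow, and this is largely right:

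- The trigger is cause, not study group. On the literal reading a death due to sampling still needs the form.
- A death correctly attributed to elective care would fail the REC's relatedness test anyway, so no REC report is lost for it. What remains is the risk of misattribution.
- Control Group 1 has a single nasosorption, and limited life expectancy is an exclusion there.
- Assessment and Follow-up plans no follow-up when sampling is well tolerated, so a later death after surgery would not be actively sought with or without the exemption.

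A third defence is that the intended text is unknown, so a fix may reverse a deliberate choice. That is a fair caution. The Sponsor and Chief Investigator must confirm what was meant.

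**Conclusion.** The inconsistency is real and is in the operative text. As written, the rule allows a death that meets the SAE definition to bypass the 24-hour form, and so possibly the Chief Investigator's relatedness judgement and the Sponsor notice. It should be corrected.

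The size is probably very small and cannot be estimated. The protocol gives no death rate, no split of Control Group 1 between outpatients and elective surgery, and no statement of the intended meaning. The viral-load comparison, sample size and analysis do not depend on it. The conclusion rests on taking the exemption at its word.

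A reader might infer more than the protocol supports:

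- **That death is always an SAE under the definition.** It is not. The opening condition already leaves out a death judged expected.
- **That deaths caused by sampling, or all deaths in Control Group 1, go unreported.** The exemption depends on cause, and the general duty to report adverse events is not waived.
- **That deaths with no link to elective care are exempt.** This would follow only if the sentence is two exemptions merged, which is conjecture.
- **That the doubled use of expectedness hides serious events.** No such event can be shown from the available text, so this is only a matter of tidy wording.

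**What to change.** Reconcile the exemption with the SAE definition. Reword the one sentence so that it covers only the planned elective admission itself, that is, the hospitalisation criterion, and exempts no death. Any participant death then goes to the Chief Investigator on the 24-hour form for a relatedness judgement, and the existing REC and Sponsor steps follow without further change. If the present wording was deliberate, the Sponsor and Chief Investigator should say so and state who attributes the cause and where that is recorded.

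As a minor edit, remove the expectedness condition from the SAE definition and keep it only in the REC filter.

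The main edit costs one sentence and an extra form only for a death that is now exempt. The minor edit costs two words. It adds no forms if nothing is listed as expected, and an unknown number if investigators apply that condition by judgement. Neither edit changes study procedures, patient care, sample size or analysis.
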